### **8.5.2 Safety Monitoring for Renal Function**

All patients will have renal function tests monitored every 2 weeks throughout the study.

In the event of appearance of symptoms or signs consistent with renal dysfunction such as hematuria, polyuria, anuria, flank pain, new-onset hypertension, nausea and/or anorexia, renal function should be tested as soon as possible. Testing at a lab that is local to the patient is permissible for this purpose.

During the course of the study, urinary surveillance will include urinalysis to include urine albumin/creatinine ratio (UACR), urine protein/creatinine ratio (UPCR) and urinary red blood cells (RBCs), as well as serum creatinine and cystatin-C to estimate glomerular filtration rate

(eGFR), which will be monitored every 2 weeks. In addition, biomarkers of acute renal injury will also be measured every 2 weeks ([Appendix B](#)).

The assessment of serum creatinine, cystatin-C, and urinalysis more frequently than every 2 weeks will be guided by consultation with a local nephrologist. Any decision taken by the Investigator to discontinue study medication will be made taking into account all available and relevant data. In addition, the decision to discontinue Study Drug may also be based on lesser changes in these parameters observed in isolation or in association with other renal-related abnormalities. Any decision taken to restart study medication will be made in consultation with the Study Medical Monitor taking into account all available and relevant data.

All renal function test results will be reviewed on an ongoing basis at the weekly safety review by the Medical Monitor.

All results of renal function tests must be reviewed promptly (within 48 hours of receipt) by the Investigator or the designee to ensure that the result has not met the stopping rules per [Section 8.6.2](#).

Lab alerts for abnormal renal tests will be issued for: Creatinine clearance (by CKD-EPI formula) decrease from baseline > 25%, urine albumin/creatinine ratio (UACR) > 250 mg/g, urine protein/creatinine ratio (UPCR) > 0.5 mg/mg, or an increase in serum creatinine from baseline > 0.3 mg/dL).

These alert levels are set to anticipate and prevent the risk of a medically significant change in renal function while receiving Study Drug.

In the event of a confirmed (as described in [Section 8.5](#)) laboratory result meeting one or more of the above criteria, dosing with the Study Drug should be interrupted and the Study Medical Monitor informed. In addition, the following supplemental renal tests should be immediately obtained:

Serum creatinine, urine culture, 24-hour urine sample for creatinine clearance, urine albumin and urine protein, urine microscopy sample with inspection of sediment.

The Investigator should also review the patient's concomitant medications for potentially nephrotoxic agents, and, with the results of these evaluations, review any decision to continue or discontinue the patient in consultation with the Study Medical Monitor and the medical area specialist consultant of the DSMB.

#### **8.5.4 Safety Monitoring for Minor Bleeding Events**

Patients will be instructed to promptly report any signs or symptoms of bleeding. Minor bleeding events are those that do not fulfill the criteria for major bleeding or clinically-relevant, non-major bleeding events (which are defined in Section 8.6.3), for example excess bruising, petechiae, or gingival bleeding on brushing teeth. If a minor bleeding event occurs, the Investigator must notify the Sponsor Medical Monitor and additional testing of coagulation parameters activated partial thromboplastin time (aPTT), prothrombin time (PT), INR, hepatic enzymes, bilirubin and platelet count should be performed.

#### **8.5.5 Safety Monitoring for Constitutional Symptoms**

Patients will be instructed to promptly report any signs or symptoms of fever, constitutional symptoms, rash, arthralgia or joint swelling that may arise during the study and the Investigator should closely evaluate all potential causes, including concomitant illness. Patients who experience persistent symptoms should be discussed with the Sponsor Medical Monitor or designee to determine whether additional monitoring or laboratory tests are required.

### **8.6 Stopping Rules**

For the purposes of stopping rules, Baseline is defined as the average of Day 1 pre-dose assessment and the last measurement prior to Day 1.

#### **8.6.1 Stopping Rules for Liver Chemistry Elevations**

In the event of confirmed laboratory results meeting any of the following criteria, dosing of a patient with Study Drug will be stopped permanently:

1. ALT or AST  $> 8 \times \text{ULN}$ , which is confirmed
2. ALT or AST  $> 5 \times \text{ULN}$ , which is confirmed and persists for  $\geq 2$  weeks

3. ALT or AST > 3 x ULN (or the greater of 2 x Baseline value or 3 x ULN if the Baseline value was > ULN), which is confirmed **and** total bilirubin > 2 x ULN or INR > 1.5
4. ALT or AST > 3 x ULN (or the greater of 2 x Baseline value or 3 x ULN if the Baseline value was > ULN), which is confirmed, and the new appearance (i.e., onset coincides with the changes in hepatic enzymes) of fatigue, nausea, vomiting, right upper quadrant pain or tenderness, fever, rash, or eosinophilia (> ULN) felt by the Investigator to be potentially related to hepatic inflammation

### **8.6.2 Stopping Rules for Renal Function Test Results**

In the event of an estimated creatinine clearance (by CKD-EPI formula) meeting any of the following criteria, or any change in renal biomarkers deemed by the nephrologist on the DSMB to require further evaluation, a serum creatinine and 24-hour urine sample for creatinine clearance and protein should be obtained:

1. CKD-EPI decrease of > 40% from Baseline
2. CKD-EPI value < 45 mL/min/1.73 m^2

Dosing of a patient with Study Drug (ISIS 681257 or placebo) will be stopped permanently if 24-hour urine testing confirms any of the following values in the absence of an alternative explanation:

1. Urine protein is > 1.0 g
2. Creatinine clearance decrease of > 40% from baseline
3. Creatinine clearance < 45 mL/min/1.73 m^2

Irrespective of whether the stopping rule is confirmed or not, the follow-up schedule and frequency of renal function monitoring after the initial event will be determined by the Study Medical Monitor in consultation with the Investigator and the medical area specialist on the DSMB. The Investigator should consider consulting a local nephrologist for any change of renal function that presents a concern. If a renal biopsy is performed, a sample specimen should be made available for examination by an independent renal pathologist who has been engaged by the Sponsor to review such specimens.

### **8.6.3 Stopping Rule for Platelet Count Results**

#### Stopping Rules for Platelet Count Results

Actions to be taken in the event of a low platelet count are summarized in [Table 3](#) below.

In the event of any platelet count less than 50,000/mm^3, or a platelet count less than 75,000/mm^3 that occurs while the patient is already on reduced dose, dosing of the patient with Study Drug will be stopped permanently (Table 3). Platelet count will be monitored daily until 2 successive values show improvement then monitored every 2-3 days until platelet count is stable.

Administration of steroids is recommended for patients whose platelet count is less than 25,000/mm^3. Recovery in platelet count may be accelerated by administration of high dose

steroids. Treatment guidelines for immune thrombocytopenia (Provan et al. 2010) recommend Dexamethasone 40 mg daily for 4 days every 2-4 weeks for 1-4 cycles; Prednis(ol)one 0.5-2 mg/kg/d for 2-4 weeks then taper; or methylprednisolone 30 mg/kg/day for 7 days (**note:** may require continuation with oral steroids after methylprednisolone).

In the event of a platelet count  $< 75,000/\text{mm}^3$  and  $> 50,000/\text{mm}^3$ , and in the absence of major bleeding or clinically-relevant non-major bleeding (defined below; Schulman et al. 2005), dosing of a patient with Study Drug should be suspended temporarily until the platelet count has recovered to  $> 100,000/\text{mm}^3$ . If dosing is continued it must be at a reduced dose as shown in Table 3. The suitability of the patient for continued dosing will be determined by the Investigator in consultation with the Study Medical Monitor and will be based on factors such as the original rate of decline in the patient's platelet count, whether any bleeding events were experienced by the patient, and the speed of recovery of platelet count after interruption of dosing.

If, after reintroduction of Study Drug, the platelet count again falls below  $75,000/\text{mm}^3$ , then dosing of the patient with Study Drug will be stopped permanently.

Once a patient commences weekly monitoring this frequency of monitoring should continue irrespective of whether the platelet count rises into the normal range.

Any unreportable platelet count result must be rechecked and determined not to have met a stopping rule before dosing can continue.

Definition of Major Bleeding Events (Schulman et al. 2005):

- Fatal bleeding, and/or
- Symptomatic bleeding in a critical area or organ, such as intracranial, intraspinal, intraocular, retroperitoneal, intraarterial or pericardial, or intramuscular with compartment syndrome, and/or
- Bleeding causing a fall in hemoglobin level of 20 g/L (1.24 mmol/L) or more within 24 hours, or leading to transfusion of 2 or more units of whole or red cells

Definition of Clinically-Relevant, Non-Major Bleeding Events (Schulman et al. 2005):

1. Multiple-source bleeding
2. Spontaneous hematoma  $> 25 \text{ cm}^2$
3. Excessive wound hematoma (not injection site related)
4. Macroscopic hematuria (spontaneous or lasting  $> 24$  hours if associated with an intervention)
5. Spontaneous rectal bleeding; epistaxis, gingival bleeding, hemoptysis, hematemesis
6. Bleeding after venipuncture for  $> 5$  minutes

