**Table 3 Actions in Patients with Low Platelet Count**

Platelet Count on Rx	Drug Dose	Monitoring
Normal range, > 140K/mm 	No action	Monitor every 2 weeks
100K-140K/mm 	No action	Closer observation Monitor every week*
75K-100K/mm 	Permanently reduce as follows: For Cohort A: reduce to 10 mg every 4 weeks For Cohort B: reduce to 20 mg every 4 weeks For Cohort C: reduce to 30 mg every 4 weeks For Cohort D: reduce to 10 mg every 2 weeks For Cohort E: reduce to 10 mg every week	Closer observation Monitor every week*
50K-75K/mm 	Pause dosing When platelet count returns to > 100K/mm  restart dosing as follows only if approved by Sponsor Medical Monitor: For Cohort A: reduce to 10 mg every 4 weeks For Cohort B: reduce to 20 mg every 4 weeks For Cohort C: reduce to 30 mg every 4 weeks For Cohort D: reduce to 10 mg every 2 week For Cohort E: reduce to 10 mg every week or Permanently discontinue Study Drug if it occurs while on already reduced dose	Closer observation Monitor every 2-3 days until 2 successive values show improvement Consider discontinuation of antiplatelet agents/non-steroidal anti-inflammatory drug (NSAIDS)/ anticoagulant medication
25K-50K/mm 	Permanently discontinue Study Drug	Closer observation: Monitor daily until 2 successive values show improvement then monitor every 2-3 days until platelet count stable Discontinue antiplatelet agents/NSAIDS/anticoagulant medication while platelet count < 50K/mm  if possible
< 25K/mm 	Permanently discontinue Study Drug	Closer observation: Monitor daily until 2 successive values show improvement then monitor every 2-3 days until platelet count stable Steroids recommended** Consider need for hospitalization and referral to hematologist Discontinue antiplatelet agents/NSAIDS/anticoagulant medication while platelet count < 50K/mm  if possible

\* Once a patient commences weekly monitoring this frequency of monitoring should continue irrespective of whether the platelet count rises into the normal range.

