## 8.8 Discontinuation of Study Drug

A patient must permanently discontinue study treatment for any of the following:

- The patient becomes pregnant. Report the pregnancy according to instructions in [Section 9.5.4](#)
- The patient withdraws consent
- The patient experiences an AE that necessitates permanent discontinuation of Study Drug
- The patient develops laboratory test abnormalities that meet any of the stopping rules listed in [Sections 8.6.1](#) to 8.6.3
- When a platelet count of less than 50,000/mm^3, or a platelet count less than 75,000/mm^3 while the patient is on a reduced dose.

The reason for discontinuation of Study Drug must be recorded in the electronic Case Report Form (eCRF) and source documentation.

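### After a permanent stop at 50,000-75,000/mm3 on a reduced dose, the Section 8.6.3 text and Table 3 order different platelet-count schedules, and Section 8.8.1 steers sites to the lighter one

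*Protocol*

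**What the plan says.** All references are to the current protocol (Amendment 4) unless stated.

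**Section 8.6.3, text.** One sentence names two triggers for a permanent stop. The first is any count below 50,000/mm3. The second is a count below 75,000/mm3 "that occurs while the patient is already on reduced dose, dosing of the patient with Study Drug will be stopped permanently". Section 8.8 repeats the second trigger ("while the patient is on a reduced dose"). The next sentence in 8.6.3 sets monitoring and does not separate the two: "Platelet count will be monitored daily until 2 successive values show improvement then monitored every 2-3 days until platelet count is stable".

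**Table 3, 50K-75K row.** This row covers two kinds of patient. One is paused from full dose and may restart at a reduced dose. The other is stopped for good: "Permanently discontinue Study Drug if it occurs while on already reduced dose". They share one monitoring interval: "Monitor every 2-3 days until 2 successive values show improvement".

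**Table 3, 25K-50K and < 25K rows.** These carry the schedule of the text: "Monitor daily until 2 successive values show improvement then monitor every 2-3 days until platelet count stable".

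**Links between them.** Section 8.6.3 introduces the table with "Actions to be taken in the event of a low platelet count are summarized in" Table 3. Section 8.8.1 has patients who discontinue early followed under the platelet rules of Table 3, located in Section 8.6.3, for the first 6 weeks.

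**The concern.** A patient already on a reduced dose whose count falls to, say, 60,000/mm3 is subject to both schedules. They differ in starting interval (daily against every 2-3 days) and in end point (a stable count against two improving values). No sentence says which prevails.

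The word used to introduce Table 3 suggests a summary of the text. Section 8.8.1, the section written for discontinued patients, nevertheless points to the table. A site following it would apply the lighter schedule, contrary to the 8.6.3 text.

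Platelet reduction is a central safety risk here. Section 2.3.3 reports marked reductions in monkeys, and the amendment history gives assessment of platelet risk as the reason for enlarging the trial to 270 patients. This patient has fallen below 75,000/mm3 despite a lower dose. What is at stake is how often a count that is not recovering gets checked, and how closely recovery is followed. Section 8.12 also requires strict adherence to the monitoring program, which is hard to audit when two schedules apply.

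**Working it through.** The protocol gives no figure to reproduce. The check sets the two schedules side by side for one patient and counts scheduled samples.

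**Inputs.** Day 0 is the draw that triggers the permanent stop. Text schedule: Section 8.6.3. Table schedule: Table 3, 50K-75K row. An interval of 2-3 days is read as any gap of 2 or 3 days. Section 8.5 asks for confirmation on a new specimen as soon as possible, ideally within 3 days. Section 8.5.3 asks for further tests promptly when the count is below 100,000/mm3, and the Appendix E list includes a citrated platelet sample and a CBC. One such draw on day 1 is therefore also credited to the table reading as a variant. Neither rule sets a repeat interval after that first sample.

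**Case 1: no improvement, days 1-6.**

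| Reading | Sampling days | Counts |
|---|---|---|
| Text | 1, 2, 3, 4, 5, 6 | 6 |
| Table row | 3, 6 up to 2, 4, 6 | 2-3 |
| Table row, day-1 draw credited | 1, 4 up to 1, 2, 4, 6 | 2-4 |

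Difference: 6 − 3 = 3 to 6 − 2 = 4 counts. With the day-1 draw credited: 6 − 4 = 2 to 6 − 2 = 4.

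**Case 2: improvement at every count, days 1-6.**

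| Reading | Sampling days | Counts |
|---|---|---|
| Text | 1, 2, 5 up to 1, 2, 4, 6 | 3-4 |
| Table row | for example 2, 4 or 3, 6 | 2 |
| Table row, day-1 draw credited | 1, 3 up to 1, 2, 4 | 2-3 |

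Difference: 1-2 counts, or 0-2 with the day-1 draw credited.

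**Case 3: after two improving values, per 7 days.** The text continues every 2-3 days until stable: days 3, 6 (2 counts) to days 2, 4, 6 (3 counts). The 50K-75K row gives no further interval of its own, but other rules normally supply a weekly floor:
- The 75K-100K and 100K-140K rows order weekly counts once the platelet count has risen into those bands.
- The footnote holds that frequency: "Once a patient commences weekly monitoring this frequency of monitoring should continue irrespective of whether the platelet count rises into the normal range". A patient reduced through the 75K-100K row was already on weekly counts. One restarted after a pause had to recover above 100,000/mm3, normally through the weekly bands.

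Difference: 2 − 1 = 1 to 3 − 1 = 2 counts per week until stable.

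**After week 6.** Section 8.8.1 relaxes monitoring only if at least 3 consecutive values are stable, as judged by the Sponsor Medical Monitor, and above 100,000/mm3. Follow-up lasts at least 12 weeks from discontinuation. This applies under either reading.

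**Resolution check.** No sentence ranks text over table. The Amendment 3 copy in the same file has the same mismatch.

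**The case against.** The best defence is that Table 3 grades monitoring by count and keeps daily checks for values below 50,000/mm3, so the 8.6.3 sentence may have been meant only for that trigger. Appendix D grades 50,000-75,000/mm3 as moderate, and the special-interest threshold in Section 9.3.3.1 is below 50,000/mm3. That intention is possible, but the sentence follows both triggers and is not limited to either. It would still need correcting.

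The practical defence carries more weight. Section 6.2.1 requires Medical Monitor instructions within 24 hours of an actionable alert, and Section 8.5 requires a full evaluation in consultation with the Medical Monitor after a confirmed stop. A site does not act on the table row alone, and one that follows the 8.6.3 text meets both rules. This limits the consequence but leaves the wording in conflict.

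Three stronger readings are tempting, and the documents do not support them:
- **The table reading requires no counts after two improving values.** The row itself is silent, but the 75K-140K rows and the footnote normally make counts weekly.
- **Nothing on the table reading demands stability.** Section 8.8.1 sets a stability test before monitoring is relaxed after week 6, whichever schedule came first.
- **Section 8.8.1 cites text and table equally, so it is neutral.** It most naturally cites Table 3 by its location. Section 8.7 joins the two with a conjunction when both are meant. Section 8.8.1 therefore favours the table, which sharpens the conflict with the text.

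**Conclusion.** The mismatch is real in the current protocol and worth correcting, but its consequence is small. It concerns only patients permanently stopped at 50,000-75,000/mm3 while on a reduced dose. For them the difference is one of interval: 6 counts against 2-3 (2-4 with a day-1 draw) over days 1-6 without improvement, a gap of 0-2 if improvement is immediate and the day-1 draw is credited, and then 2-3 counts a week against normally 1 until stable.

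The conclusion rests on reading the 8.6.3 monitoring sentence as it stands, after both triggers, and on counting from the day of the triggering draw. The weekly comparison assumes the patient reached the reduced dose through the platelet rules, or has since recovered into a weekly band. The protocol gives no rate for counts below 75,000/mm3 on a reduced dose, so no trial-wide total can be given.

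A reader might infer that such patients could go on being dosed, or that a trial result is affected. Neither follows: Study Drug is stopped under both readings, and no efficacy or sample-size result changes.

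**What to change.** Split the Table 3 50K-75K row in two:
- **Already on reduced dose, permanently discontinue:** the 8.6.3 schedule, that is, daily until two improving values in a row, then every 2-3 days until stable.
- **On full dose, pause:** the present schedule for that row.

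Section 8.8.1 can then keep its reference to Table 3, because table and text will agree.

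The edit is one table row. Measured against the table reading, the cost per affected patient is 3-4 more counts over days 1-6 without improvement (2-4 if the day-1 draw is credited), or 0-2 if improvement is immediate and that draw is credited. After two improving values it is 1-2 more per week than weekly monitoring until stable. The 8.6.3 text already orders all of these.

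If the sponsor meant daily counts only below 50,000/mm3, limit the 8.6.3 monitoring sentence to that trigger instead. That also removes the conflict. Without a stated reason for the lighter schedule, aligning to the stricter rule is the safer choice.

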**Table 3 Actions in Patients with Low Platelet Count**

Platelet Count on Rx	Drug Dose	Monitoring
Normal range, > 140K/mm 	No action	Monitor every 2 weeks
100K-140K/mm 	No action	Closer observation Monitor every week*
75K-100K/mm 	Permanently reduce as follows: For Cohort A: reduce to 10 mg every 4 weeks For Cohort B: reduce to 20 mg every 4 weeks For Cohort C: reduce to 30 mg every 4 weeks For Cohort D: reduce to 10 mg every 2 weeks For Cohort E: reduce to 10 mg every week	Closer observation Monitor every week*
50K-75K/mm 	Pause dosing When platelet count returns to > 100K/mm  restart dosing as follows only if approved by Sponsor Medical Monitor: For Cohort A: reduce to 10 mg every 4 weeks For Cohort B: reduce to 20 mg every 4 weeks For Cohort C: reduce to 30 mg every 4 weeks For Cohort D: reduce to 10 mg every 2 week For Cohort E: reduce to 10 mg every week or Permanently discontinue Study Drug if it occurs while on already reduced dose	Closer observation Monitor every 2-3 days until 2 successive values show improvement Consider discontinuation of antiplatelet agents/non-steroidal anti-inflammatory drug (NSAIDS)/ anticoagulant medication
25K-50K/mm 	Permanently discontinue Study Drug	Closer observation: Monitor daily until 2 successive values show improvement then monitor every 2-3 days until platelet count stable Discontinue antiplatelet agents/NSAIDS/anticoagulant medication while platelet count < 50K/mm  if possible
< 25K/mm 	Permanently discontinue Study Drug	Closer observation: Monitor daily until 2 successive values show improvement then monitor every 2-3 days until platelet count stable Steroids recommended** Consider need for hospitalization and referral to hematologist Discontinue antiplatelet agents/NSAIDS/anticoagulant medication while platelet count < 50K/mm  if possible

\* Once a patient commences weekly monitoring this frequency of monitoring should continue irrespective of whether the platelet count rises into the normal range.

\*\* Recovery in platelet count may be accelerated by administration of high dose steroids. Treatment guidelines for immune thrombocytopenia (Provan et al. 2010) recommend Dexamethasone 40 mg daily for 4 days every 2-4 weeks for 1-4 cycles; Prednis(ol)one 0.5-2 mg/kg/d for 2-4 weeks then taper; or Methylprednisolone 30 mg/kg/day for 7 days (note: may require continuation with oral steroids after methylprednisolone).

